#### **4.5 Safety endpoints**

Given the low-risk nature of this trial, we will adopt a targeted approach to Adverse Event (AE) and Serious Adverse Event (SAE) reporting. All AE reporting is described in detail in section 11.

#### **4.6 Stopping rules and discontinuation**

Individual participants can withdraw from the trial at any time (see section 7). The trial may be discontinued partially or stopped entirely. The rules of the trial discontinuation are described in sections 7.8, 8.9 and 15.5.

## 5 RANDOMISATION AND BLINDING

Upon entry to the trial, participants will be individually allocated in a 1:1 ratio to either proactive or reactive use of TCS. The strategies of treatment will be assigned randomly using a minimisation algorithm with a random element, balancing across groups on:

- Recruitment by site
- Age at randomisation (prepubertal – 5 to <12 years, adolescent - 12 to <16 years, adult - 16 to <45 years, perimenopausal 45 years & above)
- Time since last flare ( $\leq 6$  months,  $> 6$  months)
- Strength of study TCS (potent or superpotent)

The trial arm allocation will be concealed using a web-based algorithm and will be held on a secure server at the Nottingham Clinical Trial Unit (NCTU). The randomisation will be accessed via a secure website developed and maintained by NCTU. Unique usernames and passwords will be provided to those who are delegated the role of randomising participants using the web-based system. Randomisation can be performed by suitably trained site research staff assigned this task on the *Delegation of Responsibilities Log*, following confirmation of each individual participant's eligibility by a clinician.

### 5.1 Maintenance of randomisation codes and procedures for breaking code

The research staff randomising a participant won't be blinded to the allocation due to the nature of the treatment.

The outcomes to which an assessor will be blinded to treatment allocation will be scarring, assessed at 12 and 24 months. Global clinical severity will normally be reported by the site unblinded clinician at all time points but additionally it will be assessed by the blinded assessor at 12 and 24 months. The blinded assessor will be someone that is deemed by the PI as adequately qualified (and recorded on the delegation log) to examine and identify changes in participants with vulval LS. They will not be involved in any other trial activities. A blinded assessor will compare changes at 12 and 24 months against baseline photos or clinical assessment diagram. Where a blinded assessor is not available at the time of clinical assessment, assessment will be made subsequently by review either of the photos taken during the assessment or by comparison with the clinical diagram, and record findings. Revealing the treatment strategy allocation to the assessor should not be necessary as both involve topical steroids. However, in the unlikely scenario that assessors identify safety concerns, such as vulval cancer/pre-cancer, they will report to the site Principal Investigator (PI), who is unblinded, and who will inform NCTU as per the NCTU standard process.

The trial statisticians and Trial Steering Committee (TSC) members will be blinded to participant group allocations. An unblinded independent NCTU statistician will produce closed reports for the Data Monitoring Committee (DMC). No emergency unblinding processes are necessary. The Table 4 below describes which trial staff will be blinded/unblinded to the treatment allocation.

Table 4. Blinding status of the PEARLS trial staff

	Blinding status	Comments
Participant	Not blinded	Not practical due to trial design
Principal Investigator and other site staff	Not blinded	Not practical due to trial design
Clinical assessor at site	Blinded assessor	Scarring and global clinical severity assessment at 12 and 24 months
	Unblinded assessor	Global clinical severity at all time points and development of VIN or vulval SCC at 24 months
Chief Investigator	Blinded	The Chief Investigator will remain blinded to treatment allocation with an exception of participants recruited at their site.
Database Programmer	Not blinded	The database programmer will be responsible for the management of the randomisation system and will have access to unblinded datasets within the trial database
PEARLS Trial Management staff within NCTU	Not blinded	PEARLS Trial Management staff within NCTU will have access to the unblinded datasets within the trial database including information on treatment regimen adherence
Data Management	Not blinded	Data management staff will have access to the unblinded datasets within the trial database to ensure data quality and undertake central monitoring activities
Trial Statistician and Senior Trial Statistician	Blinded	The trial and senior trial statistician will not have access to treatment allocations or data which has the potential to unblind until after the first database lock for the analysis
Independent Statistician	Not blinded	A statistician, independent to the trial team, will be responsible for the generation of closed reports for the Data Monitoring Committee (DMC) and other potentially unblinding data and will therefore be unblinded to trial treatments

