## 2.6 Known Side Effects

Known adverse reactions to TCSs include: infection, folliculitis, paraesthesia, burning sensation, contact dermatitis, skin hypopigmentation, hypertrichosis, skin striae, acneiform dermatitis, skin atrophy, pruritus and application site pain, according to the Summary of Product Characteristics (SmPC).

TCSs are used to treat a very wide range of inflammatory skin conditions, including common conditions such as eczema, psoriasis, vitiligo as well as LS. The risk of adverse effects for potent or superpotent TCSs (such as used in this trial) is modest, but it is widely acknowledged that the fear of adverse effects is usually disproportionately high, given the relative infrequency with which such adverse effects are observed. Despite the ubiquity of topical corticosteroids in dermatological therapeutic practice, there is surprisingly little evidence to quantify the risk of adverse effects accurately. Guidelines often suggest that potent/superpotent TCSs should be used only under close clinical supervision, particularly when used in children on anatomical sites where the skin is thinner and therefore more prone to adverse effects such as atrophy.

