### Safety

- Development of vulval intraepithelial neoplasia or vulval squamous cell carcinoma at 24 months.
- Targeted adverse events e.g. stinging, skin thinning measured by patient reported symptoms and clinical examination from randomisation over 24 months.

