## 8.5 Management of study drug overdose

The risk of overdose of the TCS is very low. TCS can be safely applied to the whole body in a single dose with minimal risk of adverse reactions. There is however a risk of adverse reactions following long-term use of topical corticosteroid to localised areas of skin (e.g. skin thinning, telangiectasia) and these will be monitored during clinical examination at follow-up visits (or at an unscheduled trial visit, as necessary).

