#### **11.4 Reporting of adverse events**

Targeted adverse events will be recorded and closely monitored until resolution, stabilisation, or until it has been shown that the trial medication or treatment is not the cause.

In the PEARLS trial these targeted AEs are:

- Progression of scarring
- Pre-cancerous changes to the anatomy
- Infection (thrush and superficial bacterial infection)
- Hypersensitivity, generalised rash
- Cushing’s syndrome
- Local skin burning/skin pain and pruritus
- Allergic/contact dermatitis, erythema, rash, urticaria, local atrophic changes in the skin such as thinning, skin wrinkling, skin dryness, striae and dilatation of the superficial blood vessels (telangiectasias) may be caused by prolonged and intensive treatment with highly active corticosteroid preparations, particularly when occlusive dressings are used or when skin folds are involved.

Sites should report these events via e-CRFs.

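### Local skin atrophy, a targeted steroid harm, has no blinded reading, although a blinded assessor already assesses the vulva at 12 and 24 months

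*Protocol*

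**What the plan says.** Skin thinning is a named safety outcome. Section 4.4 (Safety) lists "Targeted adverse events e.g. stinging, skin thinning measured by patient reported symptoms and clinical examination from randomisation over 24 months". Section 11.4 makes local atrophy a targeted adverse event, naming "local atrophic changes in the skin such as thinning, skin wrinkling, skin dryness, striae and dilatation of the superficial blood vessels (telangiectasias". Section 8.5 uses thinning and telangiectasia as its examples of harm from long-term local use, to be looked for at examination: "e.g. skin thinning, telangiectasia) and these will be monitored during clinical examination at follow-up visits".

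Section 5.1 sets out what is read blind. The text says "The outcomes to which an assessor will be blinded to treatment allocation will be scarring, assessed at 12 and 24 months" and goes on to add a second, blinded reading of global severity at the same visits. Table 4 gives the blinded assessor "Scarring and global clinical severity assessment at 12 and 24 months" and the unblinded assessor "Global clinical severity at all time points and development of VIN or vulval SCC at 24 months". Of the blinded assessor, section 5.1 says "They will not be involved in any other trial activities". If no blinded assessor is present at the visit, the blinded reading is made later from photographs or the clinical diagram.

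In section 8.1, Visits 4 and 6 mark scarring and global severity as read by the blinded assessor. Adverse events appear in the same lists without that mark. Table 7 gives participant and clinician as the source for adverse effects at 3, 6, 12, 18 and 24 months. Table 3 adds medical notes and, for those under 16, parent or guardian report. Section 10.6 presents safety data descriptively, as counts and percentages by arm.

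**The concern.** The arms differ only in how the steroid is used (section 1.5), so local atrophy is a harm on which they could plausibly differ. It is also a judged sign. If everyone who records it knows the regimen, the by-arm percentages mix true occurrence with how hard each observer looked and how readily a doubtful sign was called.

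Section 2.6 makes this more than a formality. It says that "the fear of adverse effects is usually disproportionately high" and that little evidence exists to quantify the risk. The trial's own by-arm figures on atrophy will therefore carry weight for secondary objective 3, safety over 24 months. As planned, an excess in either arm could be put down to unblinded reading, and so could the absence of a difference. No analysis can later supply a blinded reading that was never taken, so this cannot be left to the analysis plan.

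**Working it through.** The documents give no atrophy rate, detection rate or target difference, so there is no figure of the plan to reproduce. The check sets the passages side by side. The arithmetic after that is illustration only.

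**Who reads atrophy?**
1. Atrophy is captured by participant report and clinical examination (section 4.4; Table 7), with medical notes and parent or guardian report as further sources (Table 3).
2. Table 4 lists participants, the principal investigator and other site staff as not blinded.
3. Table 4 assigns atrophy to neither assessor by name. The blinded assessor's remit is scarring and global severity, and section 5.1 bars other trial activities, so the clinical reading falls to unblinded staff.
4. The blinded assessor's only safety role in section 5.1 is to pass on unexpected concerns, such as suspected cancer or pre-cancer, to the unblinded principal investigator. That is not a scheduled reading of atrophy.
5. No blinded source for atrophy remains at any visit.

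**Is a blinded reader already in place?** Yes, at 12 and 24 months, for the same anatomical site. Section 5.1 requires someone qualified to examine and identify changes in vulval lichen sclerosus. The protocol already applies the same reasoning to comparable items: global severity, also a clinician's judgement, gets a second, blinded reading, and progression of scarring, itself a targeted adverse event in section 11.4, is read blind.

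**What could differential reading do?** Assumptions, none from the documents: equal true atrophy of 5% in both arms, detection of 90% in one arm and 50-70% in the other. With 400 randomised 1:1 there are 200 per arm.
- Reported rate = true rate × detection.
- Higher-detection arm: 0.05 × 0.90 = 4.5%, or 9 of 200.
- Lower-detection arm: 0.05 × 0.50 = 2.5% (5 of 200) to 0.05 × 0.70 = 3.5% (7 of 200).
- Apparent ratio: 4.5/3.5 = 1.29 to 4.5/2.5 = 1.80. If detection is keener in the reactive arm, the proactive:reactive ratio is 2.5/4.5 = 0.56 to 3.5/4.5 = 0.78.

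A second assumed mechanism is over-calling in one arm only. Reported rate = p + (1 − p) × f, where p is the common true rate and f the share of unaffected participants called positive.
- p = 5%, f = 3%: 0.05 + 0.95 × 0.03 = 7.85%, ratio 1.57.
- p = 10%, f = 1%: 0.10 + 0.90 × 0.01 = 10.9%, ratio 1.09.
- p = 2%, f = 5%: 0.02 + 0.98 × 0.05 = 6.9%, ratio 3.45.

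The ratio depends entirely on the assumptions. The illustrations show only that a spurious difference in either direction is possible with no true one.

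**The case against.** The best defence is that this is an open-label trial that names its blinded outcomes, and no passage contradicts another on the point. Safety is a secondary objective, presented descriptively, and no test or decision rule hangs on atrophy. The data monitoring committee sees safety by arm, and section 10.8 has safety analysed both by treatment received and as allocated. All of this is correct, and it limits the point to interpretation of the by-arm percentages. None of these safeguards is a blinded reading.

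Four stronger readings are tempting and are not supported:
- A reader might infer that clinicians will look harder for thinning in the proactive arm. Section 2.6 does not say whose fear is disproportionate. It also calls such effects relatively infrequent, which could as easily lead to under-calling. The direction is unknown.
- A reader might infer that a spurious excess could cancel a flare benefit. The documents offer no way to weigh the two, and the illustrated gap of 2 to 4 participants in 200 per arm is small in absolute terms.
- A reader might infer that clinicians alone record atrophy. Participants report too, equally unblinded, and their reports would stay unblinded under any fix.
- A reader might infer that the blinded assessor always examines the skin in person. Section 5.1 allows later review of photographs or the diagram, photographs are optional, and the documents do not say how often a live blinded examination will occur.

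Two objections bear on the remedy and stand. Readings at 12 and 24 months cannot replace a record that runs from randomisation over 24 months. And without a baseline rating, a sign present at 12 months cannot be told apart from one present at entry, while section 11 does not count unworsened pre-existing conditions as adverse events. Neither the Visit 1 list nor Table 7 has a baseline atrophy item.

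**Conclusion.** The point holds as a weakness of data collection. Every planned record of local atrophy comes from people who know the allocation, while a blinded assessor already assesses the vulva at 12 and 24 months, live or from images or a diagram. The by-arm comparison of atrophy is therefore open to detection bias of unknown direction and size. The apparent ratios above rest wholly on assumed rates and should not be cited as estimates.

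The conclusion rests on reading the assessor's restricted remit in section 5.1 and Table 4, with the unmarked adverse event entries in section 8.1 and Table 7, as excluding a blinded atrophy rating. No passage suggests otherwise. The primary outcome and its sample size are not affected. The change is worth making because it is cheap and cannot be made up at analysis.

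**What to change.** In sections 5.1 and 8.1 (Visits 4 and 6), Table 4 and Table 7:
- Add present/absent items, sign by sign, for the local atrophic changes of section 11.4 to the blinded assessor's form at 12 and 24 months. Have them rated after scarring and global severity, so that they cannot colour those ratings at that visit.
- Record the same items at the Visit 1 examination, before randomisation, so that new signs can be separated from existing ones.
- Keep the unblinded adverse event record at all visits. Report the blinded reading by arm beside it, not in place of it, and use it as the bias-protected comparison of atrophy at 12 and 24 months.
- Flag readings made from photographs, and record diagram-only cases as not assessable.

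The cost is a few form items at three existing visits, with no new visit, procedure or staff. There are three downsides. The blinded item will be missing or weaker where no live blinded examination takes place. Atrophy that appears and resolves between visits will be seen only in the unblinded record, as will all findings at 3, 6 and 18 months. If the same assessor returns at 24 months, the 12-month atrophy impression may carry over; rating atrophy last does not prevent that.

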## 6 TRIAL MANAGEMENT

The trial will be managed from a central coordinating centre, the Nottingham Clinical Trials Unit (NCTU), University of Nottingham. The trial will be overseen by the TSC, DMC and Trial Management Group (TMG).

The Chief Investigator has overall responsibility for the trial and shall oversee all aspects of the trial management. The data custodian will be the Chief Investigator. Chief Investigator agrees to conduct the trial in compliance with the principles outlined in the Medicines for Human Use (Clinical Trials) Regulations 2004 (SI 2004/1031), amended regulations (SI 2006/1928) and any subsequent amendments of the clinical trial regulations, GCP guidelines, the Sponsor's (and any other relevant) SOPs, and other regulatory requirements as amended.

### 6.1 Trial Committees

The trial committee terms and references will be defined in TSC/DMC/TMG charters.

#### 6.1.1 Trial Management group

The TMG will be responsible for oversight of the day-to-day management and for all aspects of the trial, including recruitment rate, budget management, safety reporting, protocol compliance and ensuring appropriate action is taken to safeguard trial participants and quality of the trial. Membership includes but is not limited to the CI, co-investigators, Trial Statisticians, Trial Manager and Data Manager. Other relevant members of the trial team will be invited to TMG meetings as required. The TMG members will meet regularly (approximately monthly) to ensure all practical details of the trial are progressing and working well.

#### 6.1.2 Trial Steering Committee

The role of the TSC is to provide overall supervision for a project on behalf of the Sponsor and Funder and to ensure that the trial is conducted to the rigorous standards set out in the Department of Health's UK Policy Framework for Health and Social Care Research and the Guidelines for Good Clinical Practice. The remit of the TSC is to provide advice, focus on trial progress and adherence to trial protocol, patient rights, safety and well-being as well as considering new information and its relevance to the research question. The TSC will also ensure that all ethical and regulatory approvals are obtained and agree proposals for significant substantial protocol amendments.

The TSC will be composed of an Independent Chair, other independent members with clinical and research expertise, along with a lay member/Patient and Public Involvement (PPI) representative. The CI will also be a member of the TSC. National Institute for Health and Care Research (NIHR) and Sponsor Representatives may be invited to attend TSC meetings as observers, if required. The TSC will adopt a charter to define its terms of reference and operation. The TSC will meet on a regular basis as specified in the TSC charter, e.g. yearly or more regularly in response to significant changes to the trial and send reports and make recommendations to the TMG/Sponsor/Funder. The TSC members will be required to sign a 'conflict of interests declaration form'.

The TSC will consider and act, as appropriate, upon the recommendations of the DMC, and in accordance with the TSC Charter.

### 6.1.3 Data Monitoring Committee

Independence is a key characteristic of a DMC where the committee members are completely uninvolved in the running of the trial and thus cannot be unfairly influenced (either directly or indirectly) by people, or institutions, involved in the trial. The role of the DMC is to monitor outcome data, safety data and other trial data and make recommendations to the TSC on whether there are any ethical or safety reasons why the trial should not continue. The safety, rights and well-being of the trial participants will be considered paramount, alongside the validity of the trial data. The DMC will also consider data emerging from other related trials, provided by the Sponsor or Funder. The DMC will operate in accordance with a trial specific charter.

The DMC will consist of an Independent Chair, an Independent Clinician and an Independent Statistician. The DMC will meet on a regular basis as specified in the DMC charter, e.g. yearly, more regularly, or on an ad-hoc basis, when a meeting may be held in urgent instances in response to safety concerns. The DMC members will be required to sign a 'conflict of interests declaration form'. Following the meetings, the DMC will make recommendations to the TSC.

### Duration of the Trial and participant involvement

Participation duration: Participants will be followed up for a minimum of 24 months from the date of their randomisation.

Recruitment duration: The expected recruitment period to the trial is 18 months (first 6 months as pilot phase).

### 6.2 End of the Trial

The end of the trial will be the date of the final database hard lock. NCTU will notify the MHRA and REC that the trial has ended within 90 days of the end of trial. Should the trial be terminated early, NCTU will inform the MHRA and REC within 15 days of the end of trial. NCTU will provide them with a summary of the clinical trial report within 12 months of the end of trial.

## 7 SELECTION AND WITHDRAWAL OF PARTICIPANTS

### 7.1 Recruitment

For illustration of recruitment pathway please refer to the trial flowchart in section 4.2.

Recruitment of trial participants will be facilitated via different routes as described below in section Screening. Trial website, social media, PPI or PPI charity groups, Be Part of Research or online health communities will be utilised to share trial details. Short animation video will be available on these platforms.

### 7.2 Screening

#### 7.2.1 Identification of potential participants at Participant Identification Centres (PICs)

PICs will be set up at GP surgeries to remove barriers to participation for those participants who would not normally attend hospital appointments for LS management. PICs, i.e. GP surgeries, will display information about the trial (e.g. posters or fliers in waiting rooms, clinical areas) to raise awareness in patients with LS and facilitate participant identification. As some patient-GP contact is still remote, this information may also be displayed online via practice website or social media groups.

PICs will conduct a search using a predefined strategy to produce a list of potential participants. The search will be done via Electronic Healthcare Record Systems, EMIS (formally known as Egton Medical Information Systems) or SystemOne and reviewed by a General Practitioner (GP) or other members of the clinical care team, to ensure that no patients have been included inappropriately and to confirm potential eligibility of patients. These patients and/or their parents or guardians will then be approached by the PICs by different methods, used at GP surgeries, including text message, email or invitation letter. Patients will be provided with the PIS, and instructions on how to express their interest in the trial and give their permission to be contacted by the secondary care site to arrange a screening visit (eligibility check). The agreement to be contacted will be tracked on the trial database. The secondary care site, which is in the catchment area of the PICs, will phone the patient to perform basic eligibility checks (e.g. symptom free, willing to travel) and ascertain their willingness to participate.

